# Study Synopsis

## TITLE

An single center, open label, randomized, prospective, phase 4 study of induction and maintenance immunosuppression in adult subjects age >18 years undergoing orthotopic liver transplantation (OLT) with basiliximab, delayed dose tacrolimus plus mycophenolate mofetil and standard of care (SOC) corticosteroids (Group 1) versus basiliximab, delayed dose tacrolimus plus mycophenolate mofetil, SOC corticosteroids, with addition of delayed maintenance everolimus at one month post OLT with subsequent mycophenolate mofetil minimization (Group 2) versus standard dose tacrolimus plus mycophenolate mofetil plus SOC corticosteroids (Group 3; control) with a high risk of developing renal dysfunction following OLT or with concomitant renal dysfunction prior to OLT.

## OBJECTIVES

To assess the efficacy and safety of basiliximab, delayed dose tacrolimus plus mycophenolate mofetil, and SOC corticosteroids versus basiliximab, delayed dose tacrolimus plus mycophenolate mofetil, and SOC corticosteroids and addition of delayed everolimus/mycophenolate minimization at one month post OLT compared to standard triple immunosuppression (tacrolimus, mycophenolate mofetil and corticosteroids) for prevention of acute organ rejection in liver transplant recipients with a high risk of developing renal dysfunction following OLT or with concomitant renal dysfunction prior to OLT.

**STUDY DESIGN:** single center, randomized, prospective, pilot

## DRUG THERAPY

### *Group 1*

Basiliximab

- Dose #1: 20mg IV within 2 hours of transplant
- Dose #2: 20mg IV Post-operative day #4

Tacrolimus (with basiliximab induction)

- Beginning day #5 post-transplant or when SCr  $\leq$  1.8 mg/dl (subjects off dialysis) to six months: 0.03-0.1mg/kg q12h PO to maintain whole blood trough concentration of 4-6ng/mL

Mycophenolate mofetil

- 500 mg po bid

Corticosteroids (SOC): Per UCLA protocol

Post-operative taper:

- Post-op day 1- methylprednisolone 50mg IVP Q6H
- Post-op day 2- methylprednisolone 40mg IVP Q6H
- Post-op day 3- methylprednisolone 30mg IVP Q6H
- Post-op day 4- methylprednisolone 20mg IVP Q6H
- Post-op day 5- methylprednisolone 20mg IVP Q12H
- Post-op day 6- methylprednisolone 10mg IVP Q12H

until taking PO, then change to: prednisone 20mg PO QAM

*Group 2*

Basiliximab

- Dose #1: 20mg IV within 2 hours of transplant
- Dose #2: 20mg IV Post-operative day #4

Tacrolimus (with basiliximab induction)

- Beginning day #5 post-transplant or when SCr  $\leq$  1.8 mg/dl (subjects off dialysis) to POD 30: 0.03-0.1mg/kg q12h PO to maintain whole blood trough concentration of 4-6ng/mL
- POD 31; reduce to tacrolimus to 2-5ng/mL in presence of everolimus levels 3-8 ng/mL

Mycophenolate mofetil

- 500 mg po bid up to POD 30: reduce mycophenolate mofetil following achievement of steady state everolimus (POD 35) as clinically indicated

Corticosteroids (SOC): Per UCLA protocol

Post-operative taper:

- Post-op day 1- methylprednisolone 50mg IVP Q6H
- Post-op day 2- methylprednisolone 40mg IVP Q6H
- Post-op day 3- methylprednisolone 30mg IVP Q6H
- Post-op day 4- methylprednisolone 20mg IVP Q6H
- Post-op day 5- methylprednisolone 20mg IVP Q12H
- Post-op day 6- methylprednisolone 10mg IVP Q12H

until taking PO, then change to: prednisone 20mg PO QAM

#### **Everolimus (delayed)**

- Add by POD 30: 1 mg po bid and adjusted to maintain whole blood trough concentrations of 3-8 ng/ml.

#### ***Group 3 (control):***

#### **Tacrolimus (without basiliximab induction)**

- Beginning day #1 post-transplant to six months: 0.03-0.1mg/kg q12h po to maintain whole blood trough concentration of 5-12ng/mL
- Six months to one year: maintain whole blood trough concentration of 5-10ng/mL

#### **Mycophenolate mofetil**

- 500 mg po bid

#### **Corticosteroids (SOC): Per UCLA protocol**

#### **Post-operative taper:**

- Post-op day 1- methylprednisolone 50mg IVP Q6H
- Post-op day 2- methylprednisolone 40mg IVP Q6H
- Post-op day 3- methylprednisolone 30mg IVP Q6H
- Post-op day 4- methylprednisolone 20mg IVP Q6H
- Post-op day 5- methylprednisolone 20mg IVP Q12H
- Post-op day 6- methylprednisolone 10mg IVP Q12H

until taking PO, then change to: prednisone 20mg PO QAM

## **PATIENT POPULATION**

In a 2:2:1 fashion, 90 subjects (group 1: n=36; group 2: n=36; group 3: n=18) will be randomized at UCLA Medical Center. Each subject will be followed for 6 months post-transplant.

## **PRIMARY ENDPOINTS**

- Assessment of the nephroprotective effects of everolimus in combination with simulect, or simulect alone following OLT at months 2, 3, 4, 5 and 6.

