## **SECONDARY ENDPOINTS**

- Mean serum creatinine, eGFR (MDRD) at weeks 1, 2, 4, 8, 12, 16, 20 and 24
- 1, 3 month and 6 month cumulative incidence of acute allograft rejection episodes, steroid resistant rejection episodes, dialysis requirements
- Incidence of death and/or graft failure at 6 months
- Tolerability and side effect profile of the combination drug therapies
- Incidence of infectious complications
- Time to first episode of acute rejection
- Refractory rejection episodes (requiring immunosuppression beyond T cell depletion)
- Rejection episodes per subjects
- Number of subjects requiring full-dose calcineurin inhibitor rescue therapy
- Monitor CD25 cell count for 3 months
- Economic analysis to determine cost-effectiveness of induction therapy with IL-2 monoclonal antibody
- Economic analysis to determine cost-effectiveness of delayed therapy with mTOR

**A three arm, single center, randomized, prospective, pilot trial of induction and maintenance immunosuppression with basiliximab, delayed dose tacrolimus plus mycophenolate mofetil, and SOC corticosteroids versus immunosuppression with basiliximab, delayed dose tacrolimus plus mycophenolate mofetil, and SOC corticosteroids with delayed addition of everolimus and mycophenolate minimization versus standard dose tacrolimus and mycophenolate mofetil plus corticosteroids in patients undergoing orthotopic liver transplantation (OLT) with concomitant renal dysfunction**

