Clearly, the primary objective assesses rate and severity of rejection, allograft loss and death as well as post-operative renal function (measured as estimated GFR). The proposed study will also evaluate the mTOR class effects (e.g., dyslipidemia, impaired wound healing and proteinuria) and in addition, it will monitor closely the potential safety effects of chronic mTOR inhibitor therapy upon infectious complications such as CMV, and HBV and HCV.

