## **Purpose**

### Primary Objectives

- To evaluate the evolution of renal function assessed by dialysis independence and time to independence from dialysis.

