## Secondary Objectives

- Glomerular Filtration Rate (eGFR); Cockcroft and Gault (MDRD)
- To determine the incidence of confirmed acute rejection episodes in patients undergoing orthotopic liver transplant at 1, 3 and 6 months post-transplant
- To determine the tolerability and adverse event profile of basiliximab, delayed dose tacrolimus, mycophenolate mofetil, SOC corticosteroids and Everolimus during the first six months post-transplant
- To determine the incidence of infectious complications during the first six months post-transplant
- To determine the time to the first episode of acute rejection
- To determine the severity of each acute rejection episode
- To determine the incidence of death and/or graft failure within the first six months post-transplant
- To determine the number of patients requiring full dose CNI rescue therapy
- To determine the mean serum creatinine concentration and eGFR: Cockcroft and Gault (MDRD) at weeks 1, 2, 4, 8, 12, 16, 20 and 24 post OLT
- To monitor CD25 cell count for the first 3 months post-transplant
- Economic analysis to determine cost-effectiveness of induction therapy with IL-2 monoclonal antibody
- Economic analysis to determine cost-effectiveness of delayed therapy with everolimus

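### Three passages define the primary differently, and neither document fixes one variable, time point, contrast or multiplicity rule

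*Protocol*

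**What the plan says.** Three places in the protocol use the word primary.

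- Synopsis, Primary Endpoints section: "Assessment of the nephroprotective effects of everolimus in combination with simulect, or simulect alone following OLT at months 2, 3, 4, 5 and 6".
- Purpose, Primary Objectives section: "To evaluate the evolution of renal function assessed by dialysis independence and time to independence from dialysis".
- Introduction, near its end: "Clearly, the primary objective assesses rate and severity of rejection, allograft loss and death as well as post-operative renal function (measured as estimated GFR").

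In the synopsis, the Objectives section, not labelled primary, takes a fourth focus: the regimens are assessed "for prevention of acute organ rejection in liver transplant recipients".

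The same measures also appear lower in the hierarchy. The synopsis Secondary Endpoints list "Mean serum creatinine, eGFR (MDRD) at weeks 1, 2, 4, 8, 12, 16, 20 and 24" and the "cumulative incidence of acute allograft rejection episodes, steroid resistant rejection episodes, dialysis requirements". Secondary Objectives list "Glomerular Filtration Rate (eGFR); Cockcroft and Gault (MDRD") and confirmed acute rejection. Renal function is also placed under Safety.

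The protocol's Statistical analysis section contains only a to-be-determined marker. The SAP is one paragraph: Mann-Whitney for continuous variables, chi-square or Fisher for categorical ones, Kaplan-Meier with log-rank for survival, all two-sided at p<0.05. It names no primary endpoint, time point, pair of arms or multiplicity rule.

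**The concern.** A reader cannot tell which result answers the trial's question. If one outcome labelled primary is null, another that carries the same label can take its place, and nothing in the documents would show the substitution.

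Two features sharpen this. The trial is open label. The SAP is dated 3 September 2020, late in the planned enrolment window, and does not settle the question. The documents do not say whether outcomes by arm had been seen by then, so this is an exposure to bias and not evidence of it.

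**Working it through.** **1. The three primaries side by side**

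| Source | Variable | Time point | Contrast |
|---|---|---|---|
| Synopsis, Primary Endpoints | none named (kidney protection in general) | five: months 2 to 6 | two experimental regimens named, no comparator |
| Purpose, Primary Objectives | two, both about coming off dialysis | none | none |
| Introduction | five: rejection rate, rejection severity, graft loss, death, eGFR | none | none |

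The first two can be read as an aim and its measure, but the second has no months 2 to 6. The third fits neither. The secondary eGFR visits at weeks 8, 12, 16, 20 and 24 are roughly months 2 to 6, so the synopsis ranks one plausible reading of its own primary endpoint as secondary.

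**2. Sample size**

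90 × 2/5, 2/5 and 1/5 = 36, 36 and 18, as stated. The total of 90 cannot be traced to any endpoint, because no effect size, SD, event rate or power is given.

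**3. False-positive chance when visit and contrast are left open**

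Inputs from the documents: n = 36/36/18, Mann-Whitney, two-sided 0.05, five monthly visits. Assumptions: one normal continuous renal variable, no true difference, equal correlation ρ between visits, and any single p<0.05 claimed as success.

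If the tests were independent, the chance is 1 − 0.95^k. With 2 contrasts × 5 visits, k = 10 gives 40.1%. With 3 × 5, k = 15 gives 53.7%. These overstate the risk because arms are shared and visits are correlated, so it was simulated (40,000 null trials per setting, normal approximation without continuity correction):

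| Setting | Two contrasts with control | All three pairs |
|---|---|---|
| One visit | 8.5–8.7% | 11.9–12.2% |
| Five visits, ρ = 0.5 | 30.0% | 40.0% |
| Five visits, ρ = 0.7 | 24.8% | 32.7% |
| Five visits, ρ = 0.9 | 17.9% | 24.3% |
| Five visits, ρ = 0.95 | 14.9% | 20.3% |

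**4. Switching between definitions**

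Take one variable from each of the three primaries and use z-tests, with an assumed correlation between variables of 0.6 down to 0. The chance of at least one p<0.05 is about 12–14% for one contrast, 19–23% for two with control and 27–32% for all three.

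**5. After the fix**

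For one variable, one visit and two contrasts with control, a fixed sequence gives 4.9–5.2%. Bonferroni or Holm gives 4.0–4.3%.

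**6. Power cost, 36 versus 18**

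Normal formula: d = (z for α/2 + z for power) × √(1/36 + 1/18).

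- α = 0.05: (1.960 + 0.842) × 0.2887 = 0.81 SD.
- α = 0.025: (2.241 + 0.842) × 0.2887 = 0.89 SD.

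Mann-Whitney needs slightly more. Simulated power is 0.80 at 0.85 SD (α = 0.05) and 0.81 at 0.95 SD (α = 0.025).

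**7. SAP timing**

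22 March 2019 to 3 September 2020 is 531 days. The planned window to 31 December 2020 is 650 days. 531/650 = 82%.

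**The case against.** - **The Purpose section supplies the measure.** The SAP's title describes adults on dialysis before transplant, for whom coming off dialysis is a natural outcome, and log-rank could analyse time to it. This makes the two renal statements easier to reconcile. But the SAP does not say so, Purpose names two variables with no time point, and the Introduction still disagrees.
- **The Introduction is narrative and the synopsis objective is not labelled primary.** Both points are fair. Without them, the labelled primary endpoint still has no variable and five time points.
- **Comparison with control is implied.** Group 3 is called the control, and the synopsis compares both regimens with standard therapy. This favours the two-contrast column over the three-pair column. But the synopsis objective also sets Group 1 against Group 2, and no order or primary contrast is given.
- **The 15–40% range covers only one variable.** This is correct: it measures freedom over visits and contrasts. Step 4 covers switching between definitions. Several of the other candidates are binary or time-to-event, so that figure is only indicative.
- **It is a pilot.** The full title reads "A three arm, single center, randomized, prospective, pilot trial of induction and maintenance immunosuppression". That lessens the need for strict error control, but it does not say which primary counts. The SAP tests everything at 0.05 and calls nothing exploratory.

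**Conclusion.** The concern holds and must be fixed. The three statements of the primary cannot all stand, and neither the protocol nor the SAP resolves them. That conclusion rests on the text alone.

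The size is conditional on assumptions the documents do not supply: the test family, the success rule and the correlations. Reading the primary as one continuous renal variable, the chance of at least one nominally significant result under no true difference is about 8.5% (two control contrasts) or 12% (three pairs) at a single visit. Over five visits it is 15–30% or 20–40% respectively, for within-patient correlation from 0.95 down to 0.5.

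**What to change.** Amend the protocol and SAP together, with a dated justification and a statement that the choice was made without reference to outcome data by arm.

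1. Name one primary variable at one time point, in the same words, in the synopsis Objectives and Primary Endpoints, the Introduction, Purpose and the SAP. Replace the placeholder in Statistical analysis with that text. If eGFR is used, name one equation: the synopsis gives MDRD alone, while Secondary Objectives writes Cockcroft and Gault beside it.
2. State the contrasts with control and control their error by a fixed sequence in a prespecified order, or by Holm or Bonferroni.
3. Report every other visit, contrast and endpoint as secondary with 95% confidence intervals. This includes the rejection, graft loss or death composite under Efficacy objectives and the month 3 and 5 rejection endpoint. Remove the chosen primary from the secondary and safety lists.

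One possible primary, offered only as an example, is a week-24 ranking: death lowest, then on dialysis, then off dialysis ordered by eGFR. It suits the planned Mann-Whitney test. It would need a rule for unknown week-24 status. The protocol plans six months of follow-up after discontinuation, but it also lists loss to follow-up and withdrawal of consent.

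Cost: no new patients or visits, and some p-values become descriptive. A fixed sequence costs nothing on the first contrast, but the second cannot be claimed if the first fails. Holm or Bonferroni raises the difference detectable with 80% power (36 versus 18) from about 0.85 SD to at most about 0.95 SD.

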## **SECONDARY ENDPOINTS**

- Mean serum creatinine, eGFR (MDRD) at weeks 1, 2, 4, 8, 12, 16, 20 and 24
- 1, 3 month and 6 month cumulative incidence of acute allograft rejection episodes, steroid resistant rejection episodes, dialysis requirements
- Incidence of death and/or graft failure at 6 months
- Tolerability and side effect profile of the combination drug therapies
- Incidence of infectious complications
- Time to first episode of acute rejection
- Refractory rejection episodes (requiring immunosuppression beyond T cell depletion)
- Rejection episodes per subjects
- Number of subjects requiring full-dose calcineurin inhibitor rescue therapy
- Monitor CD25 cell count for 3 months
- Economic analysis to determine cost-effectiveness of induction therapy with IL-2 monoclonal antibody
- Economic analysis to determine cost-effectiveness of delayed therapy with mTOR

**A three arm, single center, randomized, prospective, pilot trial of induction and maintenance immunosuppression with basiliximab, delayed dose tacrolimus plus mycophenolate mofetil, and SOC corticosteroids versus immunosuppression with basiliximab, delayed dose tacrolimus plus mycophenolate mofetil, and SOC corticosteroids with delayed addition of everolimus and mycophenolate minimization versus standard dose tacrolimus and mycophenolate mofetil plus corticosteroids in patients undergoing orthotopic liver transplantation (OLT) with concomitant renal dysfunction**

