## **Safety**

### **Renal function**

Serum creatinine, blood urea nitrogen, and serum cystatin C will be measured at all study visits and will be used to estimate the glomerular filtration rate by C/G (MDRD)

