Official Title:

A Study in Adults on Pre-LT Dialysis With Basiliximab, Delayed Tacrolimus (TAC), Mycophenolate (MMF), and Steroids (Group 1) vs. Basiliximab, Delayed TAC, MMF, Steroids, With Everolimus 30 Days Post-LT (Group 2) vs. TAC, MMF, and Steroids (Group 3)

NCT Number:

NCT04104438

Document Date:

September 3, 2020

Statistical Analysis

Continuous variables were expressed as median (range) and were compared using the Mann-Whitney U test. Categorical variables were expressed as a numerical percentage and compared by the Chi-square test or the Fishers Exact Test. Survival curves were generated by the Kaplan-Meier method, and differences in survival rates were analyzed using the Log-Rank test. All tests were two-sided, and the significance level was $p<0.05$. All analyses were performed using IBM® SPSS® Statistics version 26 (IBM Corporation, Armonk, NY).

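### The renal analyses have no rule for creatinine or eGFR taken on dialysis or for deaths, and no single eGFR equation

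*Protocol*

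**What the plan says.** The synopsis (Secondary Endpoints) lists "Mean serum creatinine, eGFR (MDRD) at weeks 1, 2, 4, 8, 12, 16, 20 and 24". The Safety section on renal function says "Serum creatinine, blood urea nitrogen, and serum cystatin C will be measured at all study visits" and that these "will be used to estimate the glomerular filtration rate by C/G (MDRD"). It makes no exception for patients on dialysis.

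Dialysis is part of this population. The inclusion criteria allow up to 45 days of it at transplant, and the SAP title reads "A Study in Adults on Pre-LT Dialysis With Basiliximab". The protocol title is wider, covering patients "with a high risk of developing renal dysfunction following OLT or with concomitant renal dysfunction prior to OLT", so the share who start on dialysis is not known. The Primary Objectives are dialysis independence and the time taken to reach it.

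The protocol's statistical section is still to be determined. The SAP is one paragraph:
- Continuous data: "Continuous variables were expressed as median (range) and were compared using the Mann-Whitney U test".
- Categorical data: "Categorical variables were expressed as a numerical percentage and compared by the Chi-square test or the Fishers Exact Test".
- Time to event: "Survival curves were generated by the Kaplan-Meier method, and differences in survival rates were analyzed using the Log-Rank test".

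It does not mention dialysis status, deaths or censoring in the renal analyses. Death with graft failure is a separate secondary endpoint. Patients who discontinue are followed to six months, which does not help with visits missed through death.

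The synopsis names MDRD. The Secondary Objectives and the efficacy objectives after the start of everolimus name Cockcroft and Gault with MDRD in brackets, and the renal function section abbreviates the same mixture.

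**The concern.** Dialysis removes creatinine. An eGFR computed from a sample taken on dialysis partly reflects the machine, so a patient with no useful kidney function can rank beside one who has recovered. The opposite default, leaving such values out, compares only patients off dialysis, a group selected after randomisation. The SAP does not choose between them, so the choice could be made after the data are seen.

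Death raises a similar problem for the primary objective. A patient who dies on dialysis can never become independent of it. Censoring that patient treats independence as still possible, so 1-KM estimates something larger than the proportion who become dialysis-free.

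Finally, two different equations are treated as one, so the eGFR variable itself is not defined.

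**Working it through.** The documents give no dialysis rate, death rate, eGFR spread or power, so there is no planned figure to reproduce. The 2:2:1 split of 90 does give 36, 36 and 18. All rates below are assumptions. The comparison shown is 36 against 18, two-sided 0.05.

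**1. eGFR comparison.** Assumed: off-dialysis eGFR mean 55 (SD 20) in both arms; apparent on-dialysis eGFR mean *m* (SD 10); the arms differ only in the share on dialysis. 6,000 simulated trials per setting.

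| On dialysis | Mann-Whitney power, values as measured, *m* = 15 / 30 / 45 / 60 | On-dialysis values ranked worst | Fisher on dialysis yes/no |
|---|---|---|---|
| 10% v 20% | 8 / 7 / 5 / 5% | 9-10% | 16% |
| 10% v 30% | 20 / 13 / 6 / 5% | 22-23% | 41% |
| 10% v 40% | 38 / 25 / 9 / 5% | 43-45% | 68% |

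At 10% v 40%, the chance that a patient in the low-dialysis arm has the better value is 0.64, 0.61, 0.55 and 0.47 at those four means. Ranked worst, it is 0.5 + 0.5 × (0.40 − 0.10) = 0.65. The loss is slight when on-dialysis values stay very low. It is complete at *m* = 55, and the direction reverses only above that. With equal dialysis shares (20% v 20%), both approaches reject about 5% of the time.

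**2. Time to dialysis independence.** Constant hazards to six months. Let *r* be the true proportion independent and *d* the proportion dying first:
- total hazard = −ln(1 − *r* − *d*)
- recovery hazard = total × *r*/(*r* + *d*)
- 1-KM with deaths censored = 1 − exp(−recovery hazard)
- survivors-only proportion = *r*/(1 − *d*)

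Example, *r* = 0.70, *d* = 0.05: total = −ln(0.25) = 1.386; recovery = 1.386 × 0.70/0.75 = 1.294; 1-KM = 1 − exp(−1.294) = 72.6%.

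| *d* | 1-KM (true 70%) | Overstatement | Survivors only | One-year death if the hazard continued |
|---|---|---|---|---|
| 2% | 71.0% | 1.0 points | 71.4% | 7% |
| 5% | 72.6% | 2.6 points | 73.7% | 17% |
| 10% | 75.5% | 5.5 points | 77.8% | 33% |

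The last column is 1 − exp(−2 × death hazard), with death hazard = total × *d*/(*r* + *d*). If both arms truly have 70%, the false gap in 1-KM is zero with equal deaths, 1.6 points at 2% v 5% and 4.6 points at 2% v 10%. For scale, the standard error of 70% in 18 patients is √(0.21/18) = 10.8 points.

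**3. Equation.** Standard forms assumed, man aged 55, creatinine 1.8 mg/dL:
- MDRD: 175 × 1.8^−1.154 × 55^−0.203 = 39.4.
- Cockcroft-Gault: (140 − 55) × weight/(72 × 1.8) = 39.4, 52.5 or 65.6 at 60, 80 or 100 kg.

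The difference at 100 kg is 65.6 − 39.4 = 26.2 units. Neither form uses cystatin C or blood urea nitrogen, both of which the renal function section lists as inputs.

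**The case against.** The strongest reply is that dialysis has outcomes of its own: independence, cumulative incidence of dialysis requirements, and renal replacement therapy. A reader might infer that the plan would hide a real dialysis difference. The documents do not support that. The SAP's own categorical test on dialysis status has more power (16, 41 and 68%) than eGFR even with dialysis ranked worst (9-10, 22-23 and 43-45%). This stands. The defect is in the validity of the eGFR comparison, not in the trial's ability to see dialysis.

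A reader might also infer that the SAP censors deaths in the analysis of dialysis independence. It does not say so. It does not assign Kaplan-Meier to that measure, and its wording about survival could mean patient and graft survival only. The overstatement is therefore conditional on the usual default. Likewise, no text proposes a survivors-only denominator.

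Nor does the SAP say that on-dialysis values are ranked. The tacrolimus start criterion ties its creatinine threshold to patients off dialysis, so exclusion is a plausible reading. But that is a dosing criterion rather than an analysis rule, and exclusion has its own selection problem.

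Finally, the larger death scenarios are heavy. In this model, 10% death before independence implies about 33% at one year if sustained, while the Introduction gives one-year survival above 85%. That figure is general background, and the same section calls pre-transplant renal dysfunction a predictor of mortality, so higher rates cannot be excluded. The documents support no particular figure.

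**Conclusion.** The omission is real and should be fixed. As written, creatinine from all visits feeds eGFR with no dialysis exception. In a population that includes dialysis patients, this makes the eGFR comparison invalid as a comparison of native kidney function. Within that comparison a dialysis difference can be diluted: slightly if on-dialysis values stay near 15, almost wholly if they approach off-dialysis values. Reversal needs on-dialysis eGFR above the off-dialysis mean.

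For the primary objective, if Kaplan-Meier is used with deaths censored, 1-KM overstates independence by about 1 to 3 points at 2-5% death before independence, and by more at higher rates. That is small beside a standard error of 10.8 points. The log-rank test with deaths censored stays valid for the cause-specific rate, so it would be wrong to conclude that the test fails; the estimated proportion is what is affected.

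The contradiction over the equation needs no assumed event rates. Its size, up to 26 units in the example, depends on body weight.

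**What to change.** 1. **Primary objective.** Among all randomised patients on dialysis at transplant, report the cumulative incidence of dialysis independence with death as a competing event. Compare the six-month proportion by the planned Chi-square/Fisher test, keeping deaths in the denominator as not independent.
2. **Creatinine and eGFR.** Do not treat a value taken on dialysis as native function. Define on dialysis by a window stated in advance (for example 7 days). In the Mann-Whitney comparison, rank those patients below all off-dialysis eGFR values and, for creatinine, as the worst values. State in advance where deaths are ranked, with a sensitivity analysis. Show deaths, dialysis and off-dialysis values separately. For change in eGFR from the start of everolimus, which is undefined for a patient on dialysis at that baseline, compare the ranked visit value instead.
3. **Equation.** Use MDRD, as in the synopsis, in the Secondary Objectives, the efficacy objectives and the renal function section. Remove cystatin C and blood urea nitrogen as inputs to it.

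**Cost.** Changes to SAP and endpoint wording, a recode of deaths, and a dialysis flag that the primary objective already needs. No extra patients or visits. The window and the rank of death are choices that must be fixed in advance, and the rank result must be read with its components. The aim is a correct estimate; no gain in power is promised.
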